5.4. Protocol Deviations

In order to closely mimic actual drug behavior in medical practice, no protocol deviation will exclude a subject from the summaries for either the ITT or safety populations.

6. ENDPOINTS AND COVARIATES

6.1. Efficacy Endpoint(s)

- The Neuropathy Impairment Score (NIS): the following subscales from the NIS will be summarized: (NIS-LL, NIS-LL-MW, NIS-LL-Reflexes, NIS-LL Sensory, NIS-LL scores for: toe, ankle, knee and hip);
Due to the fact that the full NIS was not collected in the parent studies, the NIS Total Score and NIS-UL will not be summarized for the V30M population, since there is no pre-study baseline. However, the NIS Total Score and NIS-UL will be summarized for the non-V30M population.
- The Total Quality of Life (TQOL) score as measured using the Norfolk Quality of Life for diabetic neuropathy (QOL-DN) questionnaire (including the following subscales: Total QOL, Physical Functioning/Large Fiber, Activities of Daily Living (ADLs), Symptoms, Small Fiber, Autonomic);
- The Karnofsky Performance Scale Index;
- BMI and mBMI;
- Assessment of subject ambulation.

6.2. Safety Endpoints

6.2.1. Clinical Laboratory Endpoints

The following list of clinical laboratory endpoints was collected during the course of the study. However, the summary tables will be restricted to the measures indicated with an asterisk (*). All measures will be included in the subject listings.

6.2.1.1. Serum chemistry

- a. Sodium
- b. Globulin
- c. Potassium
- d. Alkaline phosphatase (ALP)*
- e. Alanine aminotransferase (ALT)*
- f. Chloride
- g. Aspartate aminotransferase (AST)*

- h. Bicarbonate
- i. Blood urea nitrogen*
- j. Gamma glutamyl transferase*
- k. Creatinine*
- l. Cholesterol
- m. Calcium
- n. Uric acid
- o. Inorganic Phosphorous
- p. Thyroid-stimulating hormone*
- q. Glucose *
- r. Total thyroxine (T4)*
- s. Total bilirubin*
- t. Free T4*
- u. Total proteins
- v. Prealbumin (transthyretin)*
- w. Albumin*
- x. Retinol-binding protein
- y. NT-pro-BNP*
- z. Troponin I*
- aa. Troponin T*

6.2.1.2. Coagulation

- a. Prothrombin time*
- b. INR*

6.2.1.3. Hematology

- a. Hemoglobin
- b. Platelets
- c. Hematocrit
- d. White blood cell count*
- e. Red blood cell count
- f. Neutrophils*
- g. Lymphocytes*
- h. Mean corpuscular volume
- i. Monocytes*
- j. Mean corpuscular hemoglobin
- k. Eosinophils*
- l. Mean corpuscular hemoglobin concentration
- m. Basophils*

6.2.2. Urinalysis

- a. pH
- b. Blood (free Hb)

- c. Protein
- d. Nitrite
- e. Glucose
- f. Urobilinogen
- g. Ketones
- h. Specific gravity
- i. Bilirubin

6.2.3. Physical exam and Medical history

Physical exam will be listed by subject and visit in the listings. Medical history will be listed by subject.

6.2.4. ECG

ECG data will be summarized at each visit. A summary of ECG abnormalities will be presented, including changes from normal to abnormal or abnormal to normal. In addition, a summary of the number of subjects who meet the following criteria for QTc, using both the Bazett's and Frederica correction factors, will be presented:

- a change from baseline \geq 60 msec,
- a change from baseline \geq 90 msec;
- a change from baseline between 30 msec (inclusive) and $<$ 60 msec;
- a reading of greater than 450 msec at any visit;
- a reading of greater than 480 msec at any visit;
- a reading of greater than 500 msec at any visit.

6.2.5. Death

Time to death will be calculated from the first dose of the treatment (either Fx-005 or Fx1A-201), from active treatment start, and from onset of symptom, respectively. Subjects alive at the end of the study will be censored at the last visit date. For subjects who have received a liver and/or heart transplant, time will be censored at the time of transplant. Death after discontinuation will be censored at time of discontinuation. The date of onset of symptom is the start date of the earliest symptom related to ATTR in the Medical History CRF.

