### **4.1. Inclusion Criteria**

Subject eligibility should be reviewed and documented by an appropriately qualified member of the investigator's study team before subjects are included in the study.

Subjects must meet all of the following inclusion criteria to be eligible for enrollment into the study:

- Evidence of a personally signed and dated informed consent document indicating that the subject (or a legal representative) has been informed of all pertinent aspects of the study.

---

- Subject has successfully completed either Protocol Fx-006 or Fx-1A-201.
- If female, subject is post-menopausal, surgically sterilized, or willing to use an acceptable method of birth control (ie, hormonal contraceptive, intra-uterine device, diaphragm with spermicide, condom with spermicide) throughout the study and for 3 months from the end of the study. (A condom alone is not considered an acceptable method of birth control.)
- Male or female subjects with TTR-FAP who have not undergone liver or heart transplantation at time of enrollment and who have successfully completed Protocol Fx-006 or Protocol Fx1A-201.

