## **9.1. Sample Size Determination**

There is no formal sample size calculation for this protocol. Subjects who completed Protocols Fx-006 and Fx1A-201 are eligible for this study; up to 110 subjects are expected to enroll in Protocol Fx1A-303/B3461023.

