2. INTRODUCTION

This current study is being conducted to obtain additional safety and efficacy data and to provide continued dosing of tafamidis for up to 10 years, or until subject has access to tafamidis for TTR-FAP via prescription, to patients with TTR-FAP who have not undergone liver or heart transplantation and who have completed either Protocol Fx-006 (EudraCT 2008-001262-87) or Protocol Fx1A-201 (EudraCT 2007-006791-12). Upon regulatory approval for the treatment of TTR-FAP in their respective country and access to prescription tafamidis, subjects may be withdrawn from the study. The decision to withdraw subjects in a country will be done in consultation between the investigator and the sponsor. Subjects will continue to receive once-daily 20 mg tafamidis. Safety will be assessed via the incidence of treatment-emergent AEs, the use of concomitant medications, and by results from clinical laboratory testing, physical examinations, ECGs, and vital signs.

Prior to enrollment in this current study, subjects who complete Protocol Fx-006 will have received study medication for a total of 30 months (18 months of double-blinded treatment in Protocol Fx-005 plus 12 months of open-label treatment in Protocol Fx-006); subjects who complete Protocol Fx1A-201 will have received open-label tafamidis for 12 months.

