5.2. Safety Analysis Population

The safety analysis population consists of all subjects who are enrolled in this study and who have taken at least one dose of study medication.

Per the protocol, *subjects undergoing liver and/or heart transplantation while participating in this study will no longer receive investigational product. However, subjects who do undergo a liver transplant will not be withdrawn from this study and will be asked to return to the clinical unit post-transplantation on an annual basis for NIS, Norfolk QOL-DN, and Karnofsky Performance Scale Index evaluations, safety assessments, and to assess subject ambulation.* If a subject has had a liver transplant and remains in the study, that subject's data will be omitted for all post-transplant visits from the summary analyses in the ITT and safety populations.

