6.6. Baseline

The baseline for all measures will be the last measurement prior to the first dose of study drug in study Fx-005 or Fx1A-201. For the V30M subjects, an additional set of analyses will be performed using a second baseline, the last measurement prior to active treatment from study Fx-005 or Fx-006.

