8.1.3. Analyses for Time to Event Endpoints

Kaplan-Meier estimates will be computed for all time to event endpoints, including median, interquartile ranges, and 95% confidence intervals. Kaplan-Meier curves will be presented at yearly intervals. These analyses will be provided by treatment group and by TTR mutation. Separate analyses will be conducted using both measurements of baseline, at study start and at active treatment start as specified above. Additionally, a set of analyses will be done for the time from onset of symptom.

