8.3. Safety Analyses

Safety data will be summarized for the safety analysis population.

Treatment and Disposition of Subjects: Subject evaluation groups will show end of study subject disposition and will show which subjects were analyzed for efficacy, as well as for safety (adverse events and laboratory data). Frequency counts will be supplied for subject discontinuation(s) by treatment.

A listing of treatment duration for each subject will be reported in accordance with the sponsor reporting standards.

Demographic and Baseline Characteristics. A break-down of demographic data will be provided for age, gender, race, weight, body mass index, and height. Each will be summarized by treatment group, sex at birth and 'All Subjects' in accordance with the sponsor reporting standards. All baseline and disease characteristics will also be summarized.

Discontinuations. Subject discontinuations due to adverse events will be detailed and summarized.

Adverse events (AEs): Treatment emergent adverse events will be summarized by causality and severity.

Hematology, Biochemistry and Urinalysis: Descriptive statistics will be provided for each test result and for change from baseline by visit. Additional summaries for abnormalities in laboratory measures will be provided for the following populations: without regard to baseline, abnormal at baseline and normal at baseline.

Baseline is defined in two ways as described above.

ECG: Changes from baseline (defined as the last evaluation prior to the first dose of study drug) will be summarized for each of the ECG measures listed above. In addition, ECG changes from baseline will be categorized as follows:

- a change from baseline \geq 60 msec,
- a change from baseline \geq 90 msec;
- a change from baseline between 30 msec (inclusive) and $<$ 60 msec;
- a reading of greater than 450 msec at any visit;
- a reading of greater than 480 msec at any visit;
- a reading of greater than 500 msec at any visit.

Baseline is defined in two ways as described above.

Note: In Italy only Echocardiograms and Holter Monitoring were performed, and therefore, the Italian subjects will not be included in these summaries.

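### Time to death is measured from parent-study first dose, active-treatment start or symptom onset, but only in subjects who lived to enrol here, so each Kaplan-Meier curve contains time in which no death can be counted (on the active-start clock, 30 months for T-T and 12 for P-T)

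*SAP*

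**What the plan says.** - **Clocks.** SAP 6.2.5: "Time to death will be calculated from the first dose of the treatment (either Fx-005 or Fx1A-201), from active treatment start", and also from the earliest ATTR symptom in the medical history.
- **Population.** Death is listed under Safety Endpoints (SAP 6.2). SAP 8.3: "Safety data will be summarized for the safety analysis population". SAP 5.2: "The safety analysis population consists of all subjects who are enrolled in this study", with at least one dose taken. The ITT and transplant sets in Section 5 are also confined to subjects of this study.
- **Entry.** Protocol 4.1: "Subject has successfully completed either Protocol Fx-006 or Fx-1A-201". Protocol 4.2 also excludes anyone already transplanted (liver or heart).
- **Time before entry.** SAP 2: "subjects who complete Protocol Fx-006 will have received study medication for a total of 30 months". For Fx1A-201 completers it is 12 months.
- **Active start.** For V30M subjects, SAP 6.6 takes "the last measurement prior to active treatment from study Fx-005 or Fx-006". That is Fx-005 for T-T and Fx-006 for P-T.
- **Estimator.** SAP 8.1.3: "Kaplan-Meier estimates will be computed for all time to event endpoints", with medians, interquartile ranges and 95% confidence intervals, by treatment group and mutation, on both treatment clocks and from symptom onset.

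**The concern.** A subject must be alive and have completed a parent study to appear in the curve, yet the curve counts that subject as at risk from a date well before entry. This is left truncation (immortal time). On the two treatment clocks, the estimate is survival conditional on reaching entry, but it is defined as survival since treatment began. On the symptom-onset clock the pre-entry interval differs by subject, so risk sets are inflated by people who could not yet have been observed to die, and the plain estimate is biased upwards.

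The study is descriptive (SAP 4.1), so these curves, medians and intervals are themselves the result, and SAP 3 foresees their use at scientific meetings and for regulatory purposes. On the active-start clock, the display by group can show T-T surviving better than P-T when the hazards are identical.

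**Working it through.** **1. Pre-entry periods, from the documents.** Fx-005 plus Fx-006 is 18 + 12 = 30 months, which matches the SAP's figure. These are minimum periods, because the protocol allows a gap before Day 0.

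| Clock | T-T | P-T | Non-V30M |
|---|---|---|---|
| First dose | 30 months | 30 months | 12 months |
| Active start | 30 months | 12 months | 12 months |
| Symptom onset | onset to first dose + 30 | onset to first dose + 30 | onset to first dose + 12 |

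T-T and P-T differ in period length only on the active-start clock, by 30 − 12 = 18 months.

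**2. Who is left out.** Protocol Table 1 shows 65 + 63 = 128 subjects in Fx-005. Protocol 9.1: "up to 110 subjects are expected to enroll in Protocol Fx1A-303/B3461023", from both parent studies together. So at least 128 − 110 = 18 of the 128 (14%) are expected to be outside the curve, plus one more for each Fx1A-201 enrollee. The documents do not say whether any of them died.

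**3. Constant hazard, same in every group (rates assumed).** Unselected survival is S(5) = exp(−5h). With entry at time e, the planned curve gives exp(−h(5 − e)): exp(−2.5h) when e is 2.5 years and exp(−4h) when e is 1 year.

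| h per year | Unselected S(5) | Planned, e = 2.5 | Planned, e = 1 | T-T minus P-T, active start |
|---|---|---|---|---|
| 1% | 95.1% | 97.5% | 96.1% | 1.5 points |
| 2% | 90.5% | 95.1% | 92.3% | 2.8 points |
| 5% | 77.9% | 88.2% | 81.9% | 6.4 points |
| 10% | 60.7% | 77.9% | 67.0% | 10.8 points |

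On the active-start clock, e = 2.5 is T-T and e = 1 is P-T. On the first-dose clock, e = 2.5 is all V30M and e = 1 is non-V30M, and 5-year survival is overstated by 2.4, 4.6, 10.4 or 17.2 points (V30M) and 1.0, 1.8, 4.0 or 6.4 points (non-V30M). Differences are taken before rounding.

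**4. Rising hazard (assumed Weibull, shape 2, mean 10 years from onset).** H(t) = (t/11.28)², with a years from onset to first dose. The displayed gap is the planned T-T minus P-T at 5 years from active start. The real gap is the same difference without selection; it arises because P-T starts active drug later in the disease.

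| a (years) | Displayed gap | Real gap | Spurious part |
|---|---|---|---|
| 1 | 12.2 | 8.4 | 3.8 |
| 2 | 13.3 | 7.8 | 5.5 |
| 4 | 15.1 | 6.7 | 8.5 |
| 6 | 16.5 | 5.7 | 10.8 |

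**5. Symptom-onset clock (simulation, 200,000 subjects).** Assumed: onset to first dose uniform over 1 to 7 years, entry 2.5 years later, 5 years of follow-up. The earliest entry is 3.5 years, so the conditional truth at 10 years is exp(−6.5h).

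| h per year | Plain estimate at 10 years | Delayed entry | Conditional truth |
|---|---|---|---|
| 1% | 96.6% | 93.8% | 93.7% |
| 2% | 93.4% | 87.8% | 87.8% |
| 5% | 84.3% | 72.1% | 72.3% |
| 10% | 71.4% | 51.9% | 52.2% |

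If deaths between onset and entry are also allowed to thin the late entrants, the plain estimate becomes 96.5, 93.2, 83.7 or 69.5%. The conclusion is the same.

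**6. What repairs which clock.** Where a whole group enters at one fixed time, adding an entry date returns the same curve (simulated T-T at 5% per year: 0.883 either way). Delayed entry therefore helps only on the symptom-onset clock. On the treatment clocks the start point and label must change, or the missing subjects must be added.

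**The case against.** **The population is inferred.** SAP 6.2.5 and 8.1.3 name no set for time to death, and SAP 8.3 does not list it among the safety summaries. The lists of tables and figures are in separate addenda, and much of the appendix text is redacted. This stands as a limit: a conditional label there cannot be excluded. But no set in Section 5 admits a parent-study subject who did not enrol.

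**There may have been no parent-study deaths.** Non-rollover can reflect transplant, consent or eligibility, and 110 is an anticipated ceiling. This stands for the first two clocks. It does not rescue the symptom-onset clock, where plain Kaplan-Meier is wrong whenever deaths occur after staggered entry.

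**The larger figures rest on high assumed rates.** Protocol 1.2.4 reports about 187 patient-years on tafamidis. Rates of 5% and 10% imply 0.05 × 187 ≈ 9 and 0.10 × 187 ≈ 19 deaths, and that section mentions none. Silence does not establish zero, but the upper rows are best read as outer bounds. At 1 to 2% the spurious gap of 1.5 to 2.8 points is smaller than sampling error. With 65 and 63 subjects fully followed, the 95% half-width for the difference is 1.96 × √(0.975 × 0.025/65 + 0.961 × 0.039/63) ≈ 6 points at 1%, and about 8 at 2%.

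**No test is planned, and SAP 8.1.1 already recognises the 18-month misalignment.** True, but that caution covers change from baseline in annually measured outcomes. SAP 8.1.3 still requires the active-start survival display by group, without any warning.

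**Conclusion.** The point holds and should be fixed. The 30- and 12-month pre-entry periods, and the 18-month difference between T-T and P-T on the active-start clock, come from the documents. That the curves are limited to enrolled subjects is the likeliest reading of SAP 5, 6.2 and 8.3, not an explicit statement.

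The size depends on assumed death rates. Over 1 to 10% per year, the spurious 5-year gap on the active-start clock is 1.5 to 10.8 points. From first dose, the overstatement is 2.4 to 17.2 points (V30M) and 1.0 to 6.4 (non-V30M). Both are negligible if nobody died before rollover. On the symptom-onset clock, under the assumed entry pattern, the plain 10-year estimate is too high by 2.9 points at 1% (96.6 − 93.7) and 19.2 at 10% (71.4 − 52.2).

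**What to change.** Amend SAP 6.2.5 and 8.1.3, and name the analysis population for death:

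1. Start the main survival curve at Day 1 of B3461023 and label it conditional on completing the parent study.
2. On the symptom-onset clock, use a left-truncated (delayed-entry) product-limit estimate. Begin it where enough subjects are at risk, and state that it is conditional on survival to that time.
3. If a first-dose curve is kept, include everyone treated in Fx-005 and Fx1A-201 with their parent-study deaths. Censor those who did not roll over at last contact, and note that this censoring may be informative.
4. If an active-start curve is kept, include everyone who ever received active drug. State that P-T is still conditional on surviving and completing 18 months of placebo, and do not present T-T against P-T as a comparison on that clock.

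Items 1 and 2 need only SAP wording and light reprogramming, with data already held. Items 3 and 4 need parent-study death and last-contact dates. The price is that reported survival may look less favourable, and the delayed-entry curve will be imprecise early on, when few subjects are at risk.

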V30M is the most common mutation associated with TTR-FAP, with major foci of patients in Portugal, Sweden and Japan. The disease usually begins in the third or fourth decade, but the onset of symptoms may be later, particularly in Sweden. Initial symptoms include decrease in temperature and pain sensation in the lower extremities; autonomic dysfunction, including orthostatic hypotension, gastrointestinal motility disorders, impotence, and urinary retention/incontinence. As the disease progresses to involve larger myelinated fibers, muscle weakness, loss of reflexes, and the impairment of position and vibratory sensations can occur. At this stage, involvement of upper extremities becomes apparent. Although penetrance varies greatly among geographic and ethnic foci, the outcome of TTR-FAP is invariably progressive and fatal. The length of survival for patients with TTR-FAP is severely shortened. After a mean interval of 10 years from initial symptom, patients usually

---

die from progressive and relentless worsening of the neuropathy, secondary infections, cachexia or sudden death. The only currently available disease-modifying treatment option is liver transplant.

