### **6.3. Subject Withdrawal**

Subjects may withdraw from the study at any time at their own request, or they may be withdrawn at any time at the discretion of the investigator or sponsor for safety or behavioral reasons, or the inability of the subject to comply with the protocol required schedule of study visits or procedures at a given study site. In addition, the Sponsor may choose to discontinue this study, at which time all subjects will be withdrawn.

A subject may be withdrawn from the study for any of the following reasons:

- Withdrawal of consent;
- Adverse event;
- Protocol noncompliance;
- Subject lost to follow-up;
- Subject death.

Subjects who are prematurely withdrawn from the study will not be replaced. Subjects who discontinue from the study at any time following enrollment will have a final end of study visit performed, including all safety and efficacy assessments, at the time of discontinuation.

Subjects undergoing liver and or heart transplantation while participating in this study will no longer receive investigational product. However, subjects who do undergo a liver transplant will not be withdrawn from this study and will be asked to return to the clinical unit post-transplantation on an annual basis for NIS, Norfolk QOL-DN, and Karnofsky Performance Scale Index evaluations, safety assessments, and to assess subject ambulation. Further relevant information for the Investigator to consider for any subject undergoing liver transplantation is provided in [Appendix 4](#).

---

Upon regulatory approval of tafamidis for the treatment of TTR-FAP in their respective country, and access to prescription tafamidis, subjects may be withdrawn from the study. The decision to withdraw subjects in a country will be done in consultation between the investigator and the sponsor. Subjects will have all end of study procedures completed prior to study withdrawal. These subjects are considered completers.

If a subject does not return for a scheduled visit, every effort should be made to contact the subject. In any circumstance, every effort should be made to document subject outcome, if possible. The investigator should inquire about the reason for withdrawal, request the subject to return all unused investigational product(s), request the subject to return for a final visit, if applicable, and follow-up with the subject regarding any unresolved adverse events (AEs).

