5.3. Liver and/or Heart Transplant Subjects

Data for subjects who have received a liver transplant during the course of this study and who remain in the study will have their post-transplant data summarized separately.

[Appendix 2](#) will describe the summary table and listings to be produced.

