6.4. Discontinuations

All reasons for discontinuation will be summarized including: discontinuations due to adverse events, discontinuations due to laboratory abnormalities, discontinuations due to

death, discontinuations due to liver and/or heart transplant, discontinuations due to other causes (not laboratory abnormalities, death or liver transplant), and all cause discontinuation.

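### Time to death is censored at transplant and at discontinuation; this may be informative in a direction the documents do not show, and no readable analysis tests it

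*SAP*

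**What the plan says.** SAP 6.2.5 defines time to death on three clocks: from first dose in Fx-005 or Fx1A-201, from the start of active treatment, and from symptom onset. Two of its censoring rules matter here: "For subjects who have received a liver and/or heart transplant, time will be censored at the time of transplant" and "Death after discontinuation will be censored at time of discontinuation". SAP 8.1.3 specifies Kaplan-Meier estimates for every time-to-event endpoint, by treatment group and TTR mutation. It names no competing-risk analysis, composite or sensitivity analysis.

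On transplant more widely:

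- Protocol 6.3 stops study drug at liver or heart transplant but says "subjects who do undergo a liver transplant will not be withdrawn from this study"; these subjects are asked back every year.
- SAP 5.2 says of a liver-transplant subject who stays in the study that "that subject's data will be omitted for all post-transplant visits from the summary analyses in the ITT and safety populations".
- SAP 5.3 adds that liver-transplant subjects "who remain in the study will have their post-transplant data summarized separately" and refers to Appendix 2, which is redacted.
- SAP 6.4 includes "discontinuations due to liver and/or heart transplant" among the tabulated discontinuation reasons.
- Protocol 1.2 states: "The only currently available disease-modifying treatment option is liver transplant".

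**The concern.** Kaplan-Meier is valid under censoring only if, at each time, censored subjects have the same later risk as those still being followed. Leaving tafamidis for the one other disease-modifying treatment of a fatal disease is unlikely to be unrelated to prognosis. The SAP does not say which survival the curve is meant to estimate, nor what happens if the assumption fails.

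The study has no control group (Protocol 3.1), so readers will look for an outside reference. One of the SAP's clocks starts at symptom onset. Protocol 1.2 cites death a mean of 10 years after first symptom, so the two are likely to be set side by side. The curve is also shown by original Fx-005 treatment group, where unequal transplant rates could affect the contrast. SAP 3 allows interim results to go to scientific meetings or serve regulatory purposes.

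**Working it through.** The documents give no survival estimate, transplant rate or event count, so there is no plan figure to reproduce. What follows is an illustration under constant rates.

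**Inputs (all assumed)**
- *L*, death rate while at risk: 0.02, 0.05 or 0.10 per year. The top value is 1/10, from the 10-year mean in Protocol 1.2; that mean runs from first symptom, so it serves only as an upper anchor.
- *t*, transplant rate: 0.01, 0.03 or 0.05 per year.
- *θ*, death hazard after transplant relative to subjects still at risk: 0.5, 1, 2 or 4.
- *T*: 5 or 10 years (study duration is up to 10 years, Protocol 3.2).

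**Formulas**
- Kaplan-Meier censored at transplant: exp(−LT).
- Transplant-free survival: exp(−(L+t)T).
- Survival with follow-up past transplant: exp(−(L+t)T) + t[exp(−θLT) − exp(−(L+t)T)] / (L+t−θL).

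**One case in full: L = 0.05, t = 0.03, T = 10**
- Censored Kaplan-Meier: exp(−0.5) = 60.7%.
- Transplant-free survival: exp(−0.8) = 44.9%.
- Followed past transplant, θ = 2: 0.4493 + 0.03 × (0.3679 − 0.4493)/(0.08 − 0.10) = 0.4493 + 0.1222 = 57.2%. The censored curve is 3.5 points higher.
- Followed past transplant, θ = 0.5: 0.4493 + 0.03 × (0.7788 − 0.4493)/0.055 = 0.4493 + 0.1797 = 62.9%. The censored curve is 2.3 points lower.

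**L = 0.05 at 10 years; the last four columns are censored Kaplan-Meier minus survival followed past transplant, in points**

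| t per year | Transplanted by 10 y | Censored KM | Transplant-free | θ=0.5 | θ=1 | θ=2 | θ=4 |
|---|---|---|---|---|---|---|---|
| 0.01 | 7.5% | 60.7% | 54.9% | −0.8 | 0 | +1.2 | +2.8 |
| 0.03 | 20.7% | 60.7% | 44.9% | −2.3 | 0 | +3.5 | +7.9 |
| 0.05 | 31.6% | 60.7% | 36.8% | −3.5 | 0 | +5.5 | +12.2 |

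**Whole grid.** At 10 years the difference runs from −4.7 points (θ=0.5, L=0.10, t=0.05) to +12.2 (θ=4, L=0.05, t=0.05). At 5 years it runs from −1.9 to +6.7. With t = 0.01 (about 6 to 9% transplanted by 10 years) the 10-year range is −1.1 to +2.8.

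**Two readings to avoid**
- The transplant-free curve lies below the censored curve whenever a transplant occurs, even at θ = 1 where the difference in death is zero. Its gap from the death curve separates two endpoints and does not measure bias.
- Cumulative incidence of death with transplant as a competing event does not correct the curve either. Here it is (0.05/0.08) × (1 − 0.4493) = 34.4%, against 1 − 0.607 = 39.3% from the censored Kaplan-Meier. It can never be the higher of the two.

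**The case against.** The best defence is that the rule serves a coherent aim. Study drug stops at transplant, and the plan censors at discontinuation too, so the curve describes survival while on tafamidis. Counting later survival would credit transplant's effect to the drug. The study is descriptive, has no hypotheses (SAP 4.1), and lists death under safety endpoints, so no formal decision rests on it. This stands as a reason to keep the censored curve. It does not remove the independence assumption, and the SAP does not name that target.

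A reader might go further and infer that survival on tafamidis is overstated. That follows only if transplanted subjects would have died faster than those who stayed. No passage says so: Protocol 1.2 presents transplant as a treatment option, and nowhere is it described as following deterioration. If fitter or earlier-stage subjects are transplanted, the error is zero or reversed.

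A reader might also infer that post-transplant data are discarded. They are taken out of the main ITT and safety summaries but summarised separately under SAP 5.3, and transplant is a tabulated discontinuation reason. Protocol 8.2 requires serious adverse events to be reported through 28 days after last dose, and later ones when the investigator learns of them. None of this puts a post-transplant death into the survival curve.

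Nor does the point extend to the longitudinal scores. The repeated-measures model in SAP 7 and 8.1.1 uses each subject's observed pre-transplant values and assumes data are missing at random given them, which is a different and weaker assumption.

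Finally, the SAP appendices are redacted, so a sensitivity analysis there cannot be excluded. SAP 6.2.5 and 8.1.3 refer to none.

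**Conclusion.** The concern holds as a gap in specification. Censoring at transplant and at discontinuation may be informative, the target is not stated, and no readable analysis tests the assumption or counts deaths that the protocol's own follow-up can supply. The documents do not determine direction or size. The illustrative range of −4.7 to +12.2 points at 10 years rests on constant rates and on assumed death, transplant and relative-hazard values, and its sign depends wholly on θ. With few transplants the effect is small. In a descriptive, uncontrolled study this is a worthwhile low-cost improvement and does not make the planned curve invalid.

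**What to change.** In SAP 6.2.5 and 8.1.3:

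1. Keep the censored curve and label it as survival on tafamidis without transplant.
2. Beside it, on the same clocks and in the same groups, report:
   - (a) time to first of death or liver/heart transplant;
   - (b) time to death counting all known deaths, including those after transplant or discontinuation, with the censoring date for everyone else stated.
3. Give the number of transplants, and the number of deaths after transplant and after discontinuation.

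Cumulative incidence of death with transplant as a competing event may be added as a description, not as a correction.

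Cost: two derived variables and a few more tables and figures. Transplant dates are already needed for the censoring rule, and annual follow-up after liver transplant is already in the protocol.

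Downsides to state with the results:
- The composite also reflects organ availability and is a different endpoint from death, so its gap from the death curve must not be read as bias.
- Analysis (b) includes whatever effect transplant has, so it shows what happened and not what would have happened without transplant.
- Deaths after discontinuation may be incompletely known. The same may apply after heart transplant, for which Protocol 6.3 describes no annual follow-up. Report how many of these subjects have known vital status.
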